3.2.2 Imputation of Missing AE Attributes

A conservative “worst-case” strategy will be applied whenever essential AE fields are missing:

- Causality missing → the AE will be coded as treatment-related.
- Severity missing → the AE will be assigned the maximum applicable CTCAE grade.
- Outcome missing and no end date recorded → the outcome will be imputed as not recovered/not resolved.

4. Statistical Analysis Methods

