8.2.2 Severity Grading

AEs will be classified as *mild*, *moderate*, or *severe*:

- Mild events are transient or easily tolerated, do not interfere with daily activities, and require no treatment or only minimal intervention.
- Moderate events interfere to some extent with daily activities, may partially impair normal function, and generally warrant medical intervention.

- Severe events prevent normal daily activities, entail marked functional impairment, and require systemic therapy or other intensive treatment; they may be life-threatening or disabling.

Severity describes the intensity of an event and is distinct from its *seriousness*; the two attributes are assessed independently.

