8.2.3 Causality

The investigator is responsible for assessing the causality between each AE recorded in the eCRF and the investigational product. This evaluation will be based on all available information at the time of completing the eCRF and is a clinical judgement.

The causality will be classified into one of five categories based on the plausibility of a relationship between the AE and the investigational product: *related*, *very likely related*, *possibly related*, *possibly unrelated*, and *unrelated*. Events classified as *related*, *very likely related*, or *possibly related* will be considered to have a potential or cannot be excluded as related to the study treatment, and will be classified as *related*. Events categorized as *possibly unrelated* or *unrelated* will be classified as *unrelated*.

When assessing the causal relationship between an AE and the study treatment, the following factors should be considered:

Related: There is a reasonable temporal relationship; the event aligns with the known pharmacological mechanism, characteristics, or known adverse effects of the investigational product; the event is positively dechallenged; no other reasonable explanation exists for the event; and the event is positively rechallenged.

Very Likely Related: There is a reasonable temporal relationship; the event aligns with the known pharmacological mechanism, characteristics, or known adverse effects of the investigational product; the event is positively dechallenged; no other reasonable explanation exists for the event; and there is no evidence of positive rechallenge.

Possibly Related: There is a reasonable temporal relationship; there is no evidence of positive rechallenge; and the event falls into one of the following categories:

- (1) The event is consistent with the known pharmacological mechanism, characteristics, or known adverse effects of the investigational product; the event is positively dechallenged, but other plausible explanations exist.
- (2) The event is consistent with the known pharmacological mechanism, characteristics, or known adverse effects of the investigational product; there is no evidence of positive dechallenge, and no other plausible explanations exist.
- (3) The event is not consistent with the known pharmacological mechanism, characteristics, or known adverse effects of the investigational product; the event is positively dechallenged, and no other plausible explanations exist.

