8.3 AE Reporting

All clinically significant abnormalities occurring from the time the participant signs the informed consent form through to the final visit (or withdrawal visit) must be fully documented in the participant's eCRF. This includes abnormalities observed by the investigator, reported by the participant, or identified through clinical symptoms, laboratory abnormalities, or other clinically relevant findings. Abnormalities that occur during the screening period up until the administration of the study drug should be recorded as part of the participant's medical history. Abnormalities occurring after the administration of the study drug, up to the final visit, will be recorded as AEs. If a clinically significant abnormality is present at baseline and does not worsen during the study, it should not be recorded as an AE.

The investigator is responsible for the ongoing monitoring of all AEs until they resolve, return to baseline, stabilize, or no further information can be obtained. The outcome of each AE should be documented in the participant's source records.

After the AE reporting period, only SAEs that are suspected to be related to the study treatment should be reported, and these should be followed up accordingly.

AEs should be recorded using appropriate medical terminology, with a preference for a definitive medical diagnosis. If a definitive diagnosis is not available, symptoms or

signs should be used. Once a definitive diagnosis is made, the AE record should be updated to reflect the diagnosis in place of the symptoms or signs. Each AE should be documented as a single event; a diagnosis, sign, or symptom must be recorded as an individual AE. Terms such as hospitalization, surgery, and death are not considered AEs by themselves, but the underlying cause leading to these outcomes should be documented as an AE.

The investigator is responsible for grading the severity of all AEs according to the predefined categories. Additionally, the investigator should assess the seriousness and causality of each event. For SAEs, the SAE-specific fields in the eCRF must be completed.

For each AE, the following details should be recorded: the date of onset and resolution, severity, causal relationship with the study drug, possible alternative explanations (e.g., comorbidities or concomitant medications), actions taken with regard to the study treatment, any treatment administered for the AE, and the final outcome.

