4.3 Safety Analysis

4.3.1 Drug Exposure

Based on the SS, the following information will be summarized by treatment group and presented in tabular form for all study drug administration data:

- Exposure duration (days) = Last dose date during the treatment period - First dose date during the treatment period + 1
- Actual total dose administered (mg) = Total dose actually administered during the study period
- Actual dose intensity (mg/day) = Actual dose administered (mg) / Exposure duration (days)

- Compliance (%) = (Actual dose intensity (mg/day) / Planned dose intensity (mg/day)) × 100%

Planned dose intensity (mg/day) = $(7 \times 10 \text{ mg} + 35 \times 20 \text{ mg}) / 42$

4.3.2 AE

AEs will be summarized by treatment group in the safety population. Events will be coded with the MedDRA and classified by severity (mild, moderate, or severe). A TEAE is any AE that begins after the first study dose or worsens in severity relative to its pre-dose state; events with an indeterminate temporal relationship to dosing will also be considered TEAEs. All TEAEs will be individually listed, and their incidence will be tabulated and summarized descriptively.

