4.3.2.1 TEAE Summary Table

TEAE will be summarized in the safety population. For each treatment group, the number and percentage of participants with at least one TEAE will be reported, along with the corresponding figures for the following categories:

All TEAEs

Treatment-related TEAEs. Drug relatedness is defined as *possibly related*, *probably related*, or *definitely related*; TEAEs with missing relatedness will be classified as treatment-related.

- TEAEs of moderate or greater severity

Treatment-related TEAEs of moderate or greater severity

- Serious adverse events (SAEs)

Treatment-related SAEs

- SAEs of moderate or greater severity

Treatment-related SAEs of moderate or greater severity

- TEAEs resulting in death

Treatment-related TEAEs resulting in death

- TEAEs leading to permanent discontinuation of the study drug

Treatment-related TEAEs leading to permanent discontinuation

- TEAEs leading to withdrawal from the trial

Treatment-related TEAEs leading to withdrawal

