4.3.2.2 Safety Analysis of TEAEs by SOC and PT

For each treatment group, the number and percentage of participants with at least one event will be tabulated by MedDRA SOC and, within each SOC, by PT for the following categories:

TEAE category	Subcategory (Treatment-related)
All TEAEs	Treatment-related TEAEs
TEAEs of \geq moderate severity	Treatment-related TEAEs of \geq moderate severity
Serious adverse events (SAEs)	Treatment-related SAEs
TEAEs leading to death	Treatment-related TEAEs leading to death
TEAEs leading to permanent discontinuation of study drug	Treatment-related TEAEs leading to permanent discontinuation
TEAEs leading to withdrawal from the trial	Treatment-related TEAEs leading to withdrawal

Counting Rules

- For “all TEAEs” and for drug-related TEAEs, additional summaries will cross-classify events by SOC, PT, and maximum CTCAE grade.
- If a participant reports multiple events within the same SOC or PT, the participant is counted once at the highest CTCAE grade observed for that SOC or PT.

Sorting Conventions

- SOCs are ordered in descending frequency of affected participants; ties are broken alphabetically.
- Within each SOC, PTs are ordered in descending frequency; alphabetical ordering resolves any ties.

When appropriate, the incidence of TEAEs will be compared between treatment groups by calculating the relative risk and its two-sided 95% CI.

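### The SAP's adverse-event severity and causality terms do not match the protocol's: the CTCAE-based rules cannot be run as specified, and the treatment-related definition is open to miscoding

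*SAP*

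**What the plan says.** **Severity.** Protocol 8.2.2 defines three levels (mild, moderate, severe), and Protocol 8.3 adds: "The investigator is responsible for grading the severity of all AEs according to the predefined categories". SAP 4.3.2 follows this, with events "classified by severity (mild, moderate, or severe"), and several summary rows in SAP 4.3.2.1 and 4.3.2.2 are built on moderate or greater severity.

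Two other parts of the SAP use a different scale. Under the worst-case strategy of SAP 3.2.2, an event with missing severity is handled so that "the AE will be assigned the maximum applicable CTCAE grade". In SAP 4.3.2.2, for all TEAEs and for drug-related TEAEs, "additional summaries will cross-classify events by SOC, PT, and maximum CTCAE grade". The next counting rule places a participant with several events in the same SOC or PT at the highest CTCAE grade.

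**Causality.** Protocol 8.2.3 states: "The causality will be classified into one of five categories". These are *related*, *very likely related*, *possibly related*, *possibly unrelated* and *unrelated*, and the first three are grouped as related. In SAP 4.3.2.1, "Drug relatedness is defined as" *possibly related*, *probably related* or *definitely related*. Missing causality also counts as treatment-related (SAP 3.2.2 and 4.3.2.1).

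**Which text governs.** Protocol 7.3.2 gives the SAP precedence in any discrepancy. SAP section 6 declares no deviations from the analysis planned in the protocol.

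**The concern.** An SAP should let a programmer build the safety tables without choosing definitions. Here two definitions do not fit the scales that the protocol tells investigators to use.

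For severity, the imputation rule and the by-grade summaries call for a grade that no protocol procedure specifies. The SAP also disagrees with itself, since its section 4.3.2 uses three levels.

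For causality, two of the three labels that define treatment-related are not among the protocol's five, and two of the protocol's three related labels are absent from the SAP's list. Literal coding would understate drug-related events and remove the ones investigators were most certain about. Safety is the trial's only stated secondary objective (Protocol 2.1), so these breakdowns matter to the report. If the mapping is left unwritten, someone will choose it during programming, possibly after the data have been seen.

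**Working it through.** The plan states no figure on this point, so there is nothing to reproduce. The check compares the labels and then traces which tables use them.

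**Step 1: severity scale by section.**

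| Place | Scale |
|---|---|
| Protocol 8.2.2 and 8.3 | mild / moderate / severe |
| SAP 4.3.2 | mild / moderate / severe |
| SAP 4.3.2.1 and 4.3.2.2, threshold rows | moderate or greater |
| SAP 3.2.2, missing severity | maximum applicable CTCAE grade |
| SAP 4.3.2.2, additional summaries | maximum CTCAE grade |
| SAP 4.3.2.2, counting rule | highest CTCAE grade |

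Three SAP rules need a CTCAE grade: one imputation rule, one cross-classification and one counting rule. The protocol never mentions CTCAE, and neither document gives a version or a conversion from the three levels. As written, the imputed value therefore has no defined place on the recorded scale, and the by-grade summaries have no specified input.

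**Step 2: causality labels.**

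- Protocol related set: {related, very likely related, possibly related}.
- SAP related set: {possibly related, probably related, definitely related}, plus missing.
- In both: {possibly related}, 1 of 3.
- In the protocol set only: {related, very likely related}, 2 of 3.
- In the SAP set only: {probably related, definitely related}, 2 of 3; neither is among the protocol's five labels.

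Applied literally to each possible record:

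| Recorded value | Protocol 8.2.3 grouping | SAP 4.3.2.1, literal |
|---|---|---|
| related | related | not counted |
| very likely related | related | not counted |
| possibly related | related | counted |
| possibly unrelated | unrelated | not counted |
| unrelated | unrelated | not counted |
| missing | no rule given | counted |

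On this reading an event with no causality assessment is treatment-related, while one the investigator recorded as *related* is not. That runs against the conservative aim stated in SAP 3.2.2.

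**Step 3: tables reached.** SAP 4.3.2.1 lists 7 event categories, each with a treatment-related counterpart: 7 × 2 = 14 rows, of which 7 depend on the causality labels. The table in SAP 4.3.2.2 lists 6 categories, each with a treatment-related counterpart: 6 × 2 = 12, of which 6 depend on them. The additional summaries by grade depend on the severity term, and the drug-related version depends on both terms.

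**Step 4: tables not reached.** Counts irrespective of causality (all TEAEs, SAEs, deaths, permanent discontinuations, withdrawals) use neither label set. Threshold rows run on the three-level scale for recorded severity; only a record with missing severity reaches them through SAP 3.2.2. In tables not split by grade, the counting rule still counts each participant once. No efficacy analysis or hypothesis test uses these variables.

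**Step 5: number of events.** Neither document gives an expected number of adverse events, their distribution over causality labels, or a rate of missing severity. The size of any miscount cannot be estimated.

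**The case against.** The strongest reply is that the intent is clear and any competent programmer would follow it. SAP 4.3.2.2 sits under SAP 4.3.2, which names the three levels, and worst case on that scale is severe. Both documents take the top three ordered levels as related, and Protocol 8.2.3 says so explicitly. An SAP that counts even missing causality as related means to be inclusive, and a literal filter would leave two of its own three labels with no records. The precedence clause in Protocol 7.3.2 concerns an overview of planned analyses and may leave the investigator's classification in 8.2.3 intact. Moreover, *related* lists positive rechallenge among its conditions, while a severe AE or SAE leads to permanent discontinuation (Protocol 5.2 and 8.2.4), so few such events could reach that level.

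Much of this stands. The likely intent is that *very likely* corresponds to *probably* and *related* to *definitely*, and omitting the strongest categories requires a literal reading. But the mapping is not written anywhere, and it is at least arguable that the precedence clause favours the SAP's labels. The rechallenge argument does not cover *very likely related*, which needs no rechallenge.

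A reader might infer more than the documents support:

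- *That the trial does not collect CTCAE grades.* The eCRF is not among the documents. What can be said is that no protocol procedure specifies such grading.
- *That the severity table cannot be produced.* Only the version by CTCAE grade cannot be run as specified; a table by maximum three-level severity can.
- *That drug-related events will be understated.* This would follow from literal coding only, and nothing shows that the tables will be coded that way.

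**Conclusion.** The mismatch is real and should be corrected. As written, three SAP rules rely on a severity grade that the protocol does not specify, and the SAP's treatment-related definition matches one of the protocol's three related labels. The causality part is a programming risk, not a demonstrated loss of events.

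The reach is limited to the treatment-related rows, the summaries by grade and the handling of missing severity. All-cause TEAE, SAE, death, discontinuation and withdrawal counts are unaffected, as are the primary analysis, the testing hierarchy and the sample size. The number of events at stake is not estimable from the documents.

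The conclusion assumes that the eCRF follows Protocol 8.2.2, 8.2.3 and 8.3. If it also holds a CTCAE field, Protocol 8.2.2 and SAP 4.3.2 are incomplete and the sections still need to be reconciled.

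**What to change.** Amend the SAP before unblinding:

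1. SAP 3.2.2: assign missing severity to *severe* on the three-level scale.
2. SAP 4.3.2.2: replace CTCAE grade with three-level severity in both the cross-classification and the counting rule.
3. SAP 4.3.2.1: define treatment-related as *related*, *very likely related* or *possibly related*, plus missing causality.

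Check the eCRF field values against these definitions when the amendment is written.

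The cost is wording in three SAP sections. Data collection, the sample size and the efficacy analyses do not change. Because the replacement terms are the protocol's own, the edit introduces no data-driven choice.

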4.1 Study Population

4.1.1 Participant Disposition

All screened participants (i.e., those who signed the informed-consent form) will be included in the disposition analysis.

Screening failures: the number of participants who were not successfully randomized, together with the reasons for screen failure, will be reported.

Treated population: for all randomized participants, the number and percentage who received ≥ 1 dose of study medication will be summarized by treatment group.

Completion status: for all randomized participants, the number and percentage who completed treatment, completed the study, and discontinued treatment or withdrew from the study—overall and by each prespecified reason—will be summarized by treatment group.

Analysis sets: among all randomized participants, the number and percentage included in the full analysis set, per-protocol set, and safety analysis set will be summarized by treatment group.

A detailed tabular listing of subject disposition will be provided.

4.1.2 Protocol Deviations

A complete listing of participants with protocol deviations—including a classification of deviation severity—will be prepared and finalized before database lock.

Within the FAS, major protocol deviations will be summarized by treatment group and deviation category; counts and percentages will be tabulated.

4.1.3 Demographic and Baseline Characteristics

Using the FAS, demographic variables and baseline clinical characteristics will be summarized descriptively for each treatment group and presented in tabular form.

4.1.3.1 Demographics

Descriptive statistics will be generated for continuous variables—age (years), height (cm), weight (kg), body-mass index (BMI, kg/m²), BMI will be calculated as baseline weight (kg) divided by the square of baseline height (m) and waist circumference.

Categorical variables will be summarized as counts and percentages: age group (≥ 65 yr vs. < 65 yr), 24-hour mean PAC count (≥ 5000 vs. < 5000 beats per 24 hr), sex, race/ethnicity, and educational attainment.

4.1.3.2 Baseline Medical History

Counts and percentages will be reported for categorical baseline variables, including history of smoking, alcohol use, and documented allergies.

4.1.4 PAC Diagnoses

Using the FAS, the presence or absence of additional cardiac arrhythmias will be summarized descriptively by treatment group. PAC burden will be characterized with descriptive statistics for each group, and a participant-level listing of PAC diagnoses will be provided.

4.1.5 Prior and Concurrent Medical History

Within the FAS, all medical history present before or at baseline will be summarized descriptively by treatment group. Medical history will be coded with the Medical Dictionary for Regulatory Activities (MedDRA) and tabulated by System Organ Class (SOC) and Preferred Term (PT), with participant counts and corresponding percentages reported. SOCs and PTs will be ordered by overall frequency in descending order; ties will be resolved alphabetically. A complete participant-level listing of all prior and concurrent medical history will be provided.

- Prior medical history — Medical history that occurred before the first study dose (i.e., the end date of medical history the first-dose date).
- **Concurrent** medical history — medical history that were active on or after the first-dose date.

4.1.6 Prior and Concomitant Drug Therapies

Within the FAS, prior and concomitant medications will be summarized descriptively by treatment group. Prior and concomitant drug therapies will be coded with the WHO Drug Dictionary Global and tabulated by Anatomical Therapeutic Chemical (ATC) level-2 category and Preferred Name (PN). ATC level-2 categories and PNs will be ranked in descending order of overall frequency, with alphabetical ordering applied to ties. A participant-level listing of every prior and concomitant drug therapies will be provided.

Prior drug therapies — any drug therapies that occurred before the first study dose (i.e., the stop date precedes the first-dose date).

Concomitant drug therapies — any drug therapies that meets either of the following criteria: initiated on or after the first-dose date, or initiated before the first-dose date and continuing on or after that date.

Missing or incomplete start- or stop- date information will be imputed according to the procedures outlined in Section 3.2.

4.1.7 Prior and Concomitant Non- Drug Therapies

Within the FAS, all non-drug interventions administered before or during the trial will be summarized descriptively by treatment group. Each intervention will be coded with the MedDRA and tabulated by SOC and PT. SOCs and PTs will be ranked in descending

order of overall frequency, with alphabetical ordering applied to ties. A participant- level listing of every prior and concomitant non- drug therapy will also be provided.

- **Prior Non- Drug Therapy:** an non- drug intervention completed before the first administration of study drug (i.e., the stop date precedes the first- dose date).

- **Concomitant Non- Drug Therapy:** an non- drug intervention that either (i) is initiated on or after the first- dose date or (ii) is initiated before the first- dose date and continues on or after that date.

Missing or partial start- or stop- date information will be imputed according to the procedures described in Section 3.2.

